ATTACHMENT 2**Adverse Events of Interest: List of Preferred Terms**

AEOI	AEDECOD (MedDRA v20.0)
Rash AEOI	Acrodynia, Drug Eruption, Generalised erythema, Lupus miliaris disseminatus faciei, Mucocutaneous rash, Rash, Rash erythematous, Rash generalised, Rash macular, Rash maculo-papular, Rash maculovesicular, Rash morbilliform, Rash papular, Rash pruritic, Rash rubelliform, Rash scarlatiniform, Red man syndrome, Rash vesicular, Rash follicular, Rash papulosquamous, Dermatitis, Dermatitis acneiform, Dermatitis allergic , Dermatitis herpetiformis , Skin necrosis, Skin reaction
Liver AEOI/Cholestasis and jaundice of hepatic origin	Bilirubin excretion disorder, Cholaemia, Cholestasis, Cholestatic liver injury, Cholestatic pruritus, Drug-induced liver injury, Hepatitis cholestatic, Hyperbilirubinaemia, Icterus index increased, Jaundice, Jaundice cholestatic, Jaundice hepatocellular, Mixed liver injury, Ocular icterus, Parenteral nutrition associated liver disease, Deficiency of bile secretion, Yellow skin

Liver AEOI/Hepatic failure, fibrosis and cirrhosis and other liver damage related conditions

Acute hepatic failure, Acute on chronic liver failure, Acute yellow liver atrophy, Ascites, Asterixis, Bacterascites, Biliary cirrhosis, Biliary cirrhosis primary, Biliary fibrosis, Cholestatic liver injury, Chronic hepatic failure, Coma hepatic, Cryptogenic cirrhosis, Diabetic hepatopathy, Drug-induced liver injury, Duodenal varices, Gallbladder varices, Gastric variceal injection, Gastric variceal ligation, Gastric varices, Gastric varices haemorrhage, Hepatectomy, Hepatic atrophy, Hepatic calcification, Hepatic cirrhosis, Hepatic encephalopathy, Hepatic encephalopathy prophylaxis, Hepatic failure, Hepatic fibrosis, Hepatic hydrothorax, Hepatic infiltration eosinophilic, Hepatic lesion, Hepatic necrosis, Hepatic steato-fibrosis, Hepatic steatosis, Hepatitis fulminant, Hepatobiliary disease, Hepatocellular foamy cell syndrome, Hepatocellular injury, Hepatopulmonary syndrome, Hepatorenal failure, Hepatorenal syndrome, Hepatototoxicity, Intestinal varices, Liver and small intestine transplant, Liver and small intestine transplant, Liver dialysis, Liver disorder, Liver injury, Liver operation, Liver transplant, Lupoid hepatic cirrhosis, Minimal hepatic encephalopathy, Mixed liver injury, Nodular regenerative hyperplasia, Non-alcoholic fatty liver, Non-alcoholic steatohepatitis, Non-cirrhotic portal hypertension, Oedema due to hepatic disease, Oesophageal varices haemorrhage, Peripancreatic varices, Portal fibrosis, Portal hypertension, Portal hypertensive enteropathy, Portal hypertensive gastropathy, Portal vein cavernous transformation, Portal vein dilatation, Portopulmonary hypertension, Renal and liver transplant, Retrograde portal vein flow, Reye's syndrome, Reynold's syndrome, Splenic varices, Splenic varices haemorrhage, Steatohepatitis, Subacute hepatic failure, Varices oesophageal, Varicose veins of abdominal wall, Anorectal varices, Anorectal varices haemorrhage, Intrahepatic portal hepatic venous fistula, Peritoneovenous shunt, Portal shunt, Portal shunt procedure, Small-for-size liver syndrome, Spider naevus, Splenorenal shunt, Splenorenal shunt procedure, Spontaneous intrahepatic portosystemic venous shunt, Stomal varices, Portal triaditis

Liver AEOI / Liver-related investigations, signs and symptoms

Alanine aminotransferase abnormal, Alanine aminotransferase increased, Ammonia abnormal, Ammonia increased, Ascites, Aspartate aminotransferase abnormal, Aspartate aminotransferase increased, Bacterascites, Bile output abnormal, Bile output decreased, Biliary ascites, Bilirubin conjugated abnormal, Bilirubin conjugated increased, Bilirubin urine present, Biopsy liver abnormal, Blood bilirubin abnormal, Blood bilirubin increased, Blood bilirubin unconjugated increased, Bromosulphthalein test abnormal, Child-Pugh-Turcotte score abnormal, Child-Pugh-Turcotte score increased, Computerised tomogram liver, Foetor hepaticus, Galactose elimination capacity test abnormal, Galactose elimination capacity test decreased, Gamma-glutamyltransferase abnormal, Gamma-glutamyltransferase increased, Guanase increased, Hepaplastin abnormal, Hepaplastin decreased, Hepatic artery flow decreased, Hepatic congestion, Hepatic enzyme abnormal, Hepatic enzyme decreased, Hepatic enzyme increased, Hepatic function abnormal, Hepatic hydrothorax, Hepatic hypertrophy, Hepatic mass, Hepatic pain, Hepatic sequestration, Hepatic vascular resistance increased, Hepatobiliary scan abnormal, Hepatomegaly, Hepatosplenomegaly, Hyperammonaemia, Hyperbilirubinaemia, Hypercholia, Hypertransaminaemia, Kayser-Fleischer ring, Liver function test abnormal, Liver induration, Liver palpable, Liver scan abnormal, Liver tenderness, Mitochondrial aspartate aminotransferase increased, Molar ratio of total branched-chain amino acid to tyrosine, Oedema due to hepatic disease, Perihepatic discomfort, Retrograde portal vein flow, Total bile acids increased, Transaminases abnormal, Transaminases increased, Ultrasound liver abnormal, Urine bilirubin increased, X-ray hepatobiliary abnormal, 5'nucleotidase increased, Blood alkaline phosphatase abnormal, Blood alkaline phosphatase increased, Blood cholinesterase abnormal, Blood cholinesterase decreased, Deficiency of bile secretion, Glutamate dehydrogenase increased, Haemorrhagic ascites, Hepatic fibrosis marker abnormal, Hepatic fibrosis marker increased, Hypoalbuminaemia, Leucine aminopeptidase increased, Liver function test decreased, Liver function test increased, Liver iron concentration abnormal, Liver iron concentration increased, Model for end stage liver disease score abnormal, Model for end stage liver disease score increased, Periportal oedema, Peritoneal fluid protein abnormal, Peritoneal fluid protein decreased, Peritoneal fluid protein increased, Pneumobilia, Portal vein flow decreased, Portal vein pressure increased, Retinol binding protein decreased, Urobilinogen urine decreased, Urobilinogen urine increased, Liver palpable subcostal

Liver AEOI / Hepatitis, non infectious

Acute graft versus host disease in liver, Allergic hepatitis, Autoimmune hepatitis, Chronic graft versus host disease in liver, Chronic hepatitis, Graft versus host disease in liver, Hepatitis, Hepatitis acute, Hepatitis cholestatic, Hepatitis chronic active, Hepatitis chronic persistent, Hepatitis fulminant, Hepatitis toxic, Ischaemic hepatitis, Lupus hepatitis, Non-alcoholic steatohepatitis, Radiation hepatitis, Steatohepatitis, Granulomatous liver disease, Liver sarcoidosis, Portal tract inflammation

Hyperglycaemia AEOI

Acquired lipotrophic diabetes, Blood 1,5-anhydroglucitol decreased, Blood glucose increased, Diabetes complicating pregnancy, Diabetes mellitus, Diabetes mellitus inadequate control, Diabetes with hyperosmolarity, Diabetic arteritis, Diabetic coma, Diabetic hepatopathy, Diabetic hyperglycaemic coma, Diabetic hyperosmolar coma, Diabetic ketoacidosis, Diabetic ketoacidotic hyperglycaemic coma, Diabetic metabolic decompensation, Fructosamine increased, Fulminant type 1 diabetes mellitus, Gestational diabetes, Glucose tolerance impaired, Glucose tolerance impaired in pregnancy, Glucose urine present, Glycosuria, Glycosuria during pregnancy, Glycosylated haemoglobin increased, Hyperglycaemia, Hyperglycaemic seizure, Hyperglycaemic unconsciousness, Hyperosmolar hyperglycaemic state, Impaired fasting glucose, Insulin resistance, Insulin resistance syndrome, Insulin resistant diabetes, Insulin-requiring type 2 diabetes mellitus, Ketoacidosis, Ketonuria, Ketosis, Latent autoimmune diabetes in adults, Metabolic syndrome, Monogenic diabetes, Neonatal diabetes mellitus, Pancreatogenous diabetes, Type 1 diabetes mellitus, Type 2 diabetes mellitus, Type 3 diabetes mellitus, Urine ketone body present, Hyperglycaemic hyperosmolar nonketotic syndrome

Dyslipidaemia AEOI

Acquired lipoatrophic diabetes, Acquired mixed hyperlipidaemia, Apolipoprotein B/Apolipoprotein A-1 ratio increased, Autoimmune hyperlipidaemia, Blood cholesterol abnormal, Blood cholesterol decreased, Blood cholesterol esterase increased, Blood cholesterol increased, Blood triglycerides abnormal, Blood triglycerides decreased, Blood triglycerides increased, Diabetic dyslipidaemia, Dyslipidaemia, Familial hypertriglyceridaemia, Fat overload syndrome, High density lipoprotein abnormal, High density lipoprotein decreased, High density lipoprotein increased, Hypercholesterolaemia, Hyperlipidaemia, Hypertriglyceridaemia, Hypo HDL cholesterolaemia, Hypotriglyceridaemia, Intermediate density lipoprotein decreased, Intermediate density lipoprotein increased, LDL/HDL ratio decreased, LDL/HDL ratio increased, Lecithin-cholesterol acyltransferase deficiency, Lipid metabolism disorder, Lipids abnormal, Lipids decreased, Lipids increased, Lipoprotein (a) abnormal, Lipoprotein (a) decreased, Lipoprotein (a) increased, Low density lipoprotein abnormal, Low density lipoprotein decreased, Low density lipoprotein increased, Non-high-density lipoprotein cholesterol decreased, Non-high-density lipoprotein cholesterol increased, Primary hypercholesterolaemia, Remnant hyperlipidaemia, Remnant-like lipoprotein particles increased, Total cholesterol/HDL ratio abnormal, Total cholesterol/HDL ratio decreased, Total cholesterol/HDL ratio increased, Type I hyperlipidaemia, Type II hyperlipidaemia, Type IIa hyperlipidaemia, Type IIb hyperlipidaemia, Type III hyperlipidaemia, Type IV hyperlipidaemia, Type V hyperlipidaemia, Very low density lipoprotein abnormal, Very low density lipoprotein decreased, Very low density lipoprotein increased

Lipodystrophy AEOI

Body fat disorder, Facial wasting, Fat redistribution, Fat tissue decreased, HIV lipodystrophy, Lipoatrophy, Lipodystrophy acquired, Lipohypertrophy, Partial lipodystrophy

Immune reconstitution inflammatory AEOI

Immune reconstitution syndrome, Mycobacterium avium complex immune restoration disease, Immune Reconstitution Inflammatory Syndrome associated tuberculosis, Immune Reconstitution Inflammatory Syndrome associated Kaposi's sarcoma,

Coronary artery AEOI

Acute coronary syndrome, Acute myocardial infarction, Angina unstable, Blood creatine phosphokinase MB abnormal, Blood creatine phosphokinase MB increased, Coronary artery embolism, Coronary artery occlusion, Coronary artery reocclusion, Coronary artery thrombosis, Coronary bypass thrombosis, Coronary vascular graft occlusion, Kounis syndrome, Myocardial infarction, Myocardial necrosis, Myocardial reperfusion injury, Myocardial stunning, Papillary muscle infarction, Post procedural myocardial infarction, Postinfarction angina, Silent myocardial infarction, Troponin I increased, Troponin increased, Troponin T increased, Blood creatine phosphokinase abnormal, Blood creatine phosphokinase increased, Cardiac ventricular scarring, ECG electrically inactive area, ECG signs of myocardial infarction, Electrocardiogram Q wave abnormal, Electrocardiogram ST segment abnormal, Electrocardiogram ST segment elevation, Electrocardiogram ST-T segment elevation, Infarction, Myocardial necrosis marker increased, Scan myocardial perfusion abnormal, Vascular graft occlusion, Vascular stent occlusion, Vascular stent thrombosis, Angina pectoris, Angina unstable, Anginal equivalent, Arteriosclerosis coronary artery, Arteriospasm coronary, Coronary angioplasty, Coronary arterial stent insertion, Coronary artery bypass, Coronary artery disease, Coronary artery dissection, Coronary artery insufficiency, Coronary artery restenosis, Coronary artery stenosis, Coronary brachytherapy, Coronary bypass stenosis, Coronary endarterectomy, Coronary no-reflow phenomenon, Coronary ostial stenosis, Coronary revascularisation, Coronary vascular graft stenosis, Dissecting coronary artery aneurysm, ECG signs of myocardial ischaemia, External counterpulsation, Haemorrhage coronary artery, Ischaemic cardiomyopathy, Ischaemic mitral regurgitation, Microvascular coronary artery disease, Myocardial ischaemia, Percutaneous coronary intervention, Prinzmetal angina, Stress cardiomyopathy, Subclavian coronary steal syndrome, Subendocardial ischaemia, Arteriogram coronary abnormal, Cardiac stress test abnormal, Computerised tomogram coronary artery abnormal, Computerised tomogram coronary artery abnormal, Electrocardiogram ST segment depression, Electrocardiogram ST-T segment abnormal, Electrocardiogram ST-T segment depression, Electrocardiogram T wave abnormal, Electrocardiogram T wave inversion, Exercise electrocardiogram abnormal, Exercise test abnormal, Post angioplasty restenosis, Stress echocardiogram abnormal, Vascular stent restenosis, Vascular stent stenosis, Cardiac enzymes increased

Severe skin AEOI

Acute generalised exanthematous pustulosis, Cutaneous vasculitis, Dermatitis bullous, Dermatitis exfoliative, Dermatitis exfoliative generalised, Drug rash with eosinophilia and systemic symptoms, Epidermal necrosis, Erythema multiforme, Exfoliative rash, Oculomucocutaneous syndrome, Skin necrosis, Stevens-Johnson syndrome, Toxic epidermal necrolysis, Toxic skin eruption, Acquired epidermolysis bullosa, Blister, Blister rupture, Bullous impetigo, Conjunctivitis, Corneal exfoliation, Drug eruption, Epidermolysis, Epidermolysis bullosa, Fixed drug eruption, Genital ulceration, HLA-B*1502 assay positive, HLA-B*5801 assay positive, Hypopharyngeal synechiae, Lip exfoliation, Mouth ulceration, Mucocutaneous ulceration, Mucosa vesicle, Mucosal erosion, Mucosal exfoliation, Mucosal necrosis, Mucosal ulceration, Nikolsky's sign, Noninfective conjunctivitis, Oral mucosal blistering, Oral mucosal exfoliation, Oral papule, Oropharyngeal blistering, Pemphigoid, Pemphigus, Penile exfoliation, Skin erosion, Skin exfoliation, Staphylococcal scalded skin syndrome, Stomatitis, Tongue exfoliation, Vaginal exfoliation, Vaginal ulceration, Vulval ulceration, Vulvovaginal rash, Vulvovaginal ulceration, Genital ulceration

Cardiac conduction AEOI/Conduction defects

Accessory cardiac pathway, Adams-Stokes syndrome, Agonal rhythm, Atrial conduction time prolongation, Atrioventricular block, Atrioventricular block complete, Atrioventricular block first degree, Atrioventricular block second degree, Atrioventricular conduction time shortened, Atrioventricular dissociation, Bifascicular block, Brugada syndrome, Bundle branch block, Bundle branch block bilateral, Bundle branch block left, Bundle branch block right, Conduction disorder, Defect conduction intraventricular, Electrocardiogram delta waves abnormal, Electrocardiogram PQ interval prolonged, Electrocardiogram PQ interval prolonged, Electrocardiogram PR prolongation, Electrocardiogram PR shortened, Electrocardiogram QRS complex prolonged, Electrocardiogram QT prolonged, Electrocardiogram repolarisation abnormality, Lenegre's disease, Long QT syndrome, Paroxysmal atrioventricular block, Sinoatrial block, Trifascicular block, Ventricular dyssynchrony, Wolff-Parkinson-White syndrome

Cardiac conduction AEOI / Torsade de pointes/QT prolongation

Electrocardiogram QT interval abnormal, Electrocardiogram QT prolonged, Long QT syndrome, Long QT syndrome congenital, Torsade de pointes, Ventricular tachycardia

Pancreas AEOI

Amylase abnormal, Hyperlipasaemia, Pancreatic enzymes abnormality, Amylase increased, Lipase abnormal, Pancreatic enzymes abnormal, Blood trypsin increased, Lipase increased, Pancreatic enzymes increased, Hyperamylasaemia, Lipase urine increased, Cullen's sign, Grey Turner's sign, Haemorrhagic necrotic pancreatitis, Hereditary pancreatitis, Ischaemic pancreatitis, Oedematous pancreatitis, Pancreatic abscess, Pancreatic haemorrhage, Pancreatic necrosis, Pancreatic phlegmon, Pancreatic pseudocyst, Pancreatic pseudocyst drainage, Pancreatitis, Pancreatitis acute, Pancreatitis haemorrhagic, Pancreatitis necrotising, Pancreatitis relapsing, Pancreatorenal syndrome

Convulsions AEOI

Acquired epileptic aphasia, Acute encephalitis with refractory, repetitive partial seizures, Alcoholic seizure, Atonic seizures, Atypical benign partial epilepsy, Automatism epileptic, Autonomic seizure, Baltic myoclonic epilepsy, Benign familial neonatal convulsions, Benign rolandic epilepsy, Biotinidase deficiency, Change in seizure presentation, Clonic convulsion, Complex partial seizures, Convulsion in childhood, Convulsion neonatal, Convulsions local, Convulsive threshold lowered, Deja vu, Double cortex syndrome, Dreamy state, Drug withdrawal convulsions, Early infantile epileptic encephalopathy with burst-suppression, Eclampsia, Epilepsy, Epileptic aura, Epileptic psychosis, Febrile convulsion, Frontal lobe epilepsy, Generalised non-convulsive epilepsy, Generalised tonic-clonic seizure, Glucose transporter type 1 deficiency syndrome, Hemimegalencephaly, Hyperglycaemic seizure, Hypocalcaemic seizure, Hypoglycaemic seizure, Hyponatraemic seizure, Idiopathic generalised epilepsy, Infantile spasms, Juvenile myoclonic epilepsy, Lafora's myoclonic epilepsy, Lennox-Gastaut syndrome, Migraine-triggered seizure, Molybdenum cofactor deficiency, Myoclonic epilepsy, Myoclonic epilepsy and ragged-red fibres, Partial seizures, Partial seizures with secondary generalisation, Petit mal epilepsy, Polymicrogyria, Post stroke epilepsy, Post stroke seizure, Postictal headache, Postictal paralysis, Postictal psychosis, Postictal state, Post-traumatic epilepsy, Psychomotor seizures, Schizencephaly, Seizure, Seizure anoxic, Seizure cluster, Seizure like phenomena, Severe myoclonic epilepsy of infancy, Simple partial seizures, Status epilepticus, Sudden unexplained death in epilepsy, Temporal lobe epilepsy, Tonic clonic movements, Tonic convulsion, Tonic posturing, Topectomy, Uncinate fits, Convulsion, Grand mal convulsion

Ocular AEOI (for Posterior Uveitis)	Acute zonal occult outer retinopathy, Anterior chamber cell, Anterior chamber fibrin, Anterior chamber flare, Anterior chamber inflammation, Aqueous fibrin, Autoimmune retinopathy, Autoimmune uveitis, Behcet's syndrome, Birdshot chorioretinopathy, Blau syndrome, Blindness, Blindness transient, Blindness unilateral, Chemical iritis, Chorioretinitis, Chorioretinopathy, Choroiditis, Ciliary hyperaemia, Cystoid macular oedema, Cytomegalovirus chorioretinitis, Eales' disease, Endophthalmitis, Exudative retinopathy, Eye inflammation, Fuchs' syndrome, Glaucomatocyclitic crises, Iridocyclitis, Iritis, Macular oedema, Non-infectious endophthalmitis, Noninfective chorioretinitis, Noninfective retinitis, Ocular toxicity, Ocular vasculitis, Optic discs blurred, Panophthalmitis, Photophobia, Photopsia, Retinal exudates, Retinal oedema, Retinal pigment epitheliopathy, Retinal toxicity, Retinal perivascular sheathing, Retinal vasculitis, Retinitis, Subretinal fluid, Sudden visual loss, Susac's syndrome, Sympathetic ophthalmia, Traumatic iritis, Tubulointerstitial nephritis and uveitis syndrome, Uveitis, Uveitis-glaucoma-hyphaema syndrome, Vision blurred, Visual acuity reduced, Visual field defect, Visual impairment, Vitreal cells, Vitreous floaters, Vitreous opacities, Vitritis, Vogt-Koyanagi-Harada syndrome
Renal AEOI (for PRT) / laboratory related events	Aminoaciduria, Beta-N-acetyl D glucosaminidase increased, Hyperphosphaturia, Renal glycosuria, Acquired aminoaciduria, Hyperchloraemia , Protein urine, Protein urine present, Proteinuria, Urine phosphorus abnormal, Beta-N-acetyl D glucosaminidase abnormal, Blood chloride increased, Blood phosphorus decreased, Blood potassium decreased, Blood uric acid abnormal, Blood uric acid decreased, Glucose urine present, Glycosuria, Hyperuricosuria, Hypokalaemia, Hypophosphataemia, Urine amino acid level abnormal, Urine amino acid level increased, Urine phosphorus increased, Urine uric acid abnormal, Urine uric acid increased
Renal AEOI (for PRT) / clinical events	Polydipsia, Polyuria, Nephropathy toxic, Renal tubular disorder, Chronic kidney disease, Fanconi syndrome, Fanconi syndrome acquired, Renal tubular acidosis
Bone AEOI (for fractures) / Osteomalacia	Hypophosphataemic rickets, Osteomalacia, Renal osteodystrophy , Renal rickets, Rickets
Bone AEOI (for fractures) / Bone Loss/atrophy	Bone atrophy, Bone decalcification, Bone density decreased, Bone formation decreased, Bone loss, Craniotabes, High turnover osteopathy, Hungry bone syndrome, Osteodystrophy, Osteolysis, Osteoporosis circumscripta cranii, Osteopenia, Senile osteoporosis , Osteoporosis, Cementoplasty
Bone AEOI (for fractures) / Fracture, possibly osteoporotic	Femoral neck fracture, Hip fracture, Lumbar vertebral fracture, Osteoporotic fracture, Spinal compression fracture, Spinal fracture, Thoracic vertebral fracture

Bone AEOI (for fractures) / Fracture other

Acetabulum fracture, Ankle fracture, Atypical femur fracture, Atypical fracture, Avulsion fracture, Cervical vertebral fracture, Chance fracture, Clavicle fracture, Closed fracture manipulation, Comminuted fracture, Complicated fracture, Compression fracture, Elevation skull fracture, Epiphyseal fracture, External fixation of fracture, Femur fracture, Fibula fracture, Foot fracture, Forearm fracture, Fracture, Fracture delayed union, Fracture displacement, Fracture malunion, Fracture nonunion, Fracture pain, Fracture reduction, Fracture treatment, Fracture treatments (excl skull and spine), Fractured ischium, Fractured sacrum, Fractured coccyx, Greenstick fracture, Hand fracture, Humerus fracture, Ilium fracture, Internal fixation of fracture, Limb fracture, Lower limb fracture, Multiple fractures, Open reduction of fracture, Open reduction of spinal fracture, Osteochondral fracture, Osteosynthesis, Patella fracture, Pathological fracture, Pelvic fracture, Periprosthetic fracture, Pubis fracture, Radius fracture, Rib fracture, Sacroiliac fracture, Scapula fracture, Skull fracture, Skull fractured base, Spinal fusion fracture, Sternal fracture, Stress fracture, Tibia fracture, Torus fracture, Traumatic fracture, Ulna fracture, Upper limb fracture, Wrist fracture

Bone AEOI (for fractures) / Other Bone Events

Bone density abnormal, Bone disorder, Bone erosion, Bone lesion, Bone formation test abnormal, Bone fragmentation, Bone metabolism disorder, Bone pain, Bone resorption test abnormal, Bone scan abnormal, Bone development abnormal, Bone swelling, Epiphysiolysis, Nuclear magnetic resonance imaging spinal abnormal, Osteonecrosis, Osteonecrosis of jaw, Secondary sequestrum, Skeletal injury, Skeletal survey abnormal, Skull X-ray abnormal, Spinal X-ray abnormal, Vertebral lesion, Vertebral wedging, X-ray limb abnormal, X-ray of pelvis and hip abnormal, Bone densitometry

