5.4. Adverse Events

5.4.1. Definitions

Reported AE parameters and grades are based on the Division of AIDS Table for Grading the Severity of Adult and Pediatric Adverse Events ("**DAIDS AE grading table**"). All AEs will be coded using MedDRA version 20.0.

Events of interest

The EOIs groups include a broad list of terms to identify potential cases. The list of all preferred terms belonging to each AEOI group is provided in [Attachment 2](#).

Since many of the terms used to identify potential cases are clinically non-specific, only those retrieved cases that upon medical review are specifically suggestive of /compatible with the AEs of special interest will be commented on in the CSR.

Adverse events of interest (AEOI) groups used for the safety analyses are the following:

- Renal AEOI (for PRT)
Subgroups: laboratory related events,
clinical events
- Bone AEOI (for fractures)
Subgroups: Osteomalacia,
Bone Loss/atrophy,

Fracture, possibly osteoporotic,
Fracture other,
Other Bone Events

- Lipid-related AEOI
- Liver AEOI
- Hyperglycemia AEOI
- Pancreas AEOI
- Severe skin AEOI
- Rash AEOI
- Immune reconstitution inflammatory AEOI
- Coronary artery AEOI
- Ocular AEOI (for posterior uveitis)
- Lipodystrophy AEOI
- Cardiac conduction AEOI
Subgroups: Conduction defects,
Torsade de pointes/QT prolongation
- Convulsion AEOI

Adverse Drug Reaction (ADR)

ADRs will be presented. A list of all ADRs is in the [Attachment 3](#). The medical assessment of the safety data was performed according to a pre-specified algorithm and. In case multiple lists are available (US and EU definitions), ADRs will be tabulated separately per list.

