ATTACHMENT 3**ADR grouped Terms**

AE preferred terms (as available in AE Clinical database) are assigned an Adverse Drug Reaction System Organ Class (ADRSOC) and Adverse Drug Reaction (ADRCAT) according to the table below.

Adverse Drug Reaction System Organ Class	Adverse Drug Reaction	Adverse Event Preferred Term
GASTROINTESTINAL DISORDERS	ABDOMINAL DISTENSION	ABDOMINAL DISTENSION
	ABDOMINAL PAIN	ABDOMINAL PAIN
		ABDOMINAL PAIN LOWER
		ABDOMINAL PAIN UPPER
	DIARRHOEA	DIARRHOEA
		FREQUENT BOWEL MOVEMENTS
	DYSPEPSIA	DYSPEPSIA
	FLATULENCE	FLATULENCE
	NAUSEA	NAUSEA
	PANCREATITIS ACUTE	PANCREATITIS
		PANCREATITIS ACUTE
	VOMITING	VOMITING
	GENERAL DISORDERS AND ADMINISTRATION SITE CONDITIONS	ASTHENIA
FATIGUE		FATIGUE
HEPATOBIILIARY DISORDERS	ACUTE HEPATITIS	HEPATITIS
		HEPATITIS ACUTE
		HEPATOTOXICITY
IMMUNE SYSTEM DISORDERS	(DRUG) HYPERSENSITIVITY	DRUG HYPERSENSITIVITY
		HYPERSENSITIVITY
	IMMUNE RECONSTITUTION SYNDROME	IMMUNE RECONSTITUTION INFLAMMATORY SYNDROME
		IMMUNE RECONSTITUTION SYNDROME
METABOLISM AND NUTRITION DISORDERS	ANOREXIA	DECREASED APPETITE
	DIABETES MELLITUS	DIABETES MELLITUS
		DIABETES MELLITUS INADEQUATE CONTROL
		TYPE 2 DIABETES MELLITUS
		GLUCOSE TOLERANCE IMPAIRED
	LIPODYSTROPHY	FACIAL WASTING

		FAT REDISTRIBUTION
		FAT TISSUE INCREASED
		LIPOATROPHY
		LIPODYSTROPHY ACQUIRED
		LIPOHYPERTROPHY
		PARTIAL LIPODYSTROPHY
MUSCULOSKELETAL AND CONNECTIVE TISSUE DISORDERS	MYALGIA	MYALGIA
	OSTEONECROSIS	OSTEONECROSIS
NERVOUS SYSTEM DISORDERS	HEADACHE	HEADACHE
PSYCHIATRIC DISORDERS	ABNORMAL DREAMS	ABNORMAL DREAMS
REPRODUCTIVE SYSTEM AND BREAST DISORDERS	GYNAECOMASTIA	GYNAECOMASTIA
		HYPERTROPHY BREAST
SKIN AND SUBCUTANEOUS TISSUE DISORDERS	ANGIOEDEMA	ALLERGIC OEDEMA
		ANGIOEDEMA
		CIRCUMORAL OEDEMA
		CONJUNCTIVAL OEDEMA
		CORNEAL OEDEMA
		EPIGLOTTIC OEDEMA
		EYE OEDEMA
		EYE SWELLING
		EYELID OEDEMA
		FACE OEDEMA
		GINGIVAL OEDEMA
		GINGIVAL SWELLING
		GLEICH'S SYNDROME
		HEREDITARY ANGIOEDEMA
		LARYNGEAL OEDEMA
		LARYNGOTRACHEAL OEDEMA
		LIP OEDEMA
		LIP SWELLING
		OCULORESPIRATORY SYNDROME
		OEDEMA MOUTH
		OROPHARYNGEAL SWELLING
		PALATAL OEDEMA

		PERIORBITAL OEDEMA
		PHARYNGEAL OEDEMA
		SCLERAL OEDEMA
		SMALL BOWEL ANGIOEDEMA
		SWELLING FACE
		SWOLLEN TONGUE
		TONGUE OEDEMA
		TRACHEAL OEDEMA
	PRURITUS	PRURIGO
		PRURITUS
		PRURITUS GENERALISED
	RASH	GENERALISED ERYTHEMA
		RASH
		RASH ERYTHEMATOUS
		RASH GENERALISED
		RASH MACULAR
		RASH MACULO-PAPULAR
		RASH MORBILLIFORM
		RASH PAPULAR
		RASH PRURITIC

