	STEVENS-JOHNSON SYNDROME	STEVENS-JOHNSON SYNDROME
	TOXIC EPIDERMAL NECROLYSIS	TOXIC EPIDERMAL NECROLYSIS
	URTICARIA	URTICARIA
		URTICARIA CHRONIC
		URTICARIA PAPULAR
		URTICARIA CHOLINERGIC
		IDIOPATHIC URTICARIA
	Acute generalized exanthematous pustulosis Drug reaction with eosinophilia and systemic symptoms	Acute generalized exanthematous pustulosis Drug reaction with eosinophilia and systemic symptoms

ATTACHMENT 4

List of AE Preferred Terms (MedDRA v 20.0) for Vital Signs Blood Pressure and Heart Rate

- Blood pressure abnormal
- Blood pressure decreased
- Blood pressure abnormal
- Blood pressure diastolic abnormal
- Blood pressure diastolic decreased
- Blood pressure diastolic increased
- Blood pressure increased
- Blood pressure systolic abnormal
- Blood pressure systolic decreased
- Blood pressure systolic increased
- Blood pressure abnormal
- Labile blood pressure
- Accelerated hypertension
- Diastolic hypertension
- Essential hypertension
- Labile hypertension
- Malignant hypertension
- Systolic hypertension
- Diastolic hypotension
- Hypotension
- Heart rate abnormal
- Heart rate decreased
- Heart rate increased
- Heart rate irregular
- Bradycardia
- Tachycardia

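### The SAP's lists for events of interest and adverse drug reactions disagree on IRIS, DRESS, AGEP and fat tissue terms, so the two grouped safety tables can count the same case differently

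*SAP*

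**What the plan says.** SAP Section 5.4.1 fixes the dictionary: "All AEs will be coded using MedDRA version 20.0". It describes the AEOI groups as broad sets of terms for finding potential cases and points to Attachment 2 for every preferred term in each group. Only cases retrieved this way and judged compatible on medical review are to be discussed in the clinical study report.

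The column of terms in Attachment 2 is labelled as the coded AE term in MedDRA v20.0. Attachment 3 maps preferred terms, as held in the clinical database, to ADR categories. Section 5.4.2 plans summaries and incidence tables for both groupings. It also plans tables by system organ class and preferred term for all treatment-emergent AEs, serious AEs, grade 3 or 4 AEs and AEs for which medication was stopped.

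The entries at issue are:

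- **IRIS.** The AEOI group opens with "Immune reconstitution syndrome, Mycobacterium avium complex immune restoration disease, Immune Reconstitution Inflammatory Syndrome associated tuberculosis" and has one further term, the form associated with Kaposi's sarcoma. The ADR list has "IMMUNE RECONSTITUTION INFLAMMATORY SYNDROME" and *Immune reconstitution syndrome*.
- **DRESS.** The Severe skin AEOI has "Drug rash with eosinophilia and systemic symptoms"; the ADR list has "Drug reaction with eosinophilia and systemic symptoms".
- **AGEP.** It is spelled *generalised* in the Severe skin AEOI and *generalized* in the ADR list.
- **Fat changes.** The Lipodystrophy AEOI begins "Body fat disorder, Facial wasting, Fat redistribution, Fat tissue decreased". The lipodystrophy ADR category has "FAT TISSUE INCREASED" instead of the decrease.

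Attachment 4 is headed "List of AE Preferred Terms (MedDRA v 20.0) for Vital Signs Blood Pressure and Heart Rate". No section of the SAP refers to it.

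**The concern.** Both groupings select events by preferred term, and all events are coded in one dictionary version. If a term is absent from a list, or written in a form the dictionary does not use, an event coded to the true term is not selected.

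The AEOI list has a second role: it is the retrieval step before medical review. A case that is not retrieved does not reach the review that decides what the study report discusses under that heading.

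This matters most for the severe skin reactions. Protocol Section 1.2 names DRESS and AGEP among the post-marketing reactions to darunavir. Protocol Section 9.5.2 counts both as grade 3 rash, for which study medication is discontinued. A zero for either in one grouped table, beside a case in the other, would mislead a reader who looked at only one.

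**Working it through.** No sample size, power or error rate is involved. The check compares the lists as sets of terms, ignoring upper and lower case.

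| Group | In both lists | Attachment 2 (AEOI) only | Attachment 3 (ADR) only |
|---|---|---|---|
| IRIS (4 v 2 terms) | Immune reconstitution syndrome | the *M. avium* complex, tuberculosis and Kaposi's sarcoma forms | Immune reconstitution inflammatory syndrome |
| Lipodystrophy (9 v 7 terms) | facial wasting, fat redistribution, lipoatrophy, lipodystrophy acquired, lipohypertrophy, partial lipodystrophy | body fat disorder, fat tissue decreased, HIV lipodystrophy | fat tissue increased |
| Severe skin (four terms compared) | Stevens-Johnson syndrome, toxic epidermal necrolysis | DRESS as *Drug rash*; AGEP with *s* | DRESS as *Drug reaction*; AGEP with *z* |

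The totals reconcile. For IRIS, 1 + 3 = 4 AEOI terms and 1 + 1 = 2 ADR terms. For lipodystrophy, 6 + 3 = 9 and 6 + 1 = 7.

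Consequence for one coded event, if the lists are followed as written:

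1. **IRIS.** An event coded to the plain inflammatory term counts 1 in the ADR table and 0 in the AEOI table. An event coded to *Immune reconstitution syndrome* counts 1 in both. The loss is confined to one term, but it is the term after which the AEOI group is named.
2. **DRESS.** If version 20.0 has a single preferred term, at most one of the two wordings can equal it. One table counts 1 and the other 0. The documents do not show which wording is the coded one, so the table that fails cannot be identified.
3. **AGEP.** The event is in both lists. It is lost from one table only if matching is by exact text. The other ADR terms with this word, such as *Rash generalised*, use the *s* spelling, so the *z* form looks like a slip.
4. **Fat changes.** *Fat tissue increased* misses the AEOI table. *Fat tissue decreased*, *Body fat disorder* and *HIV lipodystrophy* miss the ADR table.

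Attachment 4 was checked separately. It has 26 entries, of which 24 are distinct, because *Blood pressure abnormal* appears three times (26 - 2 = 24). It contains six qualified hypertension terms and plain *Hypotension*, but not plain *Hypertension*.

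**The case against.** The strongest reply is that none of these events leaves the safety analysis. Section 5.4.2 tabulates every treatment-emergent AE by system organ class and preferred term. A DRESS or AGEP case that led to stopping medication should also appear in the table of AEs for which medication was stopped. This stands. A reader might infer that these events vanish from safety reporting, and the documents do not support that.

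The two lists also need not be identical. Section 5.4.1 makes the AEOI groups broad searches and says the ADR assessment followed a pre-specified algorithm, with possibly separate US and EU lists. This stands in part. It could explain why *Fat tissue decreased* is off the ADR list. It does not explain a broad IRIS search without the plain IRIS term, or two wordings for DRESS under one dictionary.

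The dictionary is not among the documents, and the protocol itself uses both wordings of DRESS (Section 1.2 and Section 9.5.2). The DRESS point therefore rests on there being one preferred term.

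Two further inferences are tempting but unsupported:

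- **That fat gain is not an event of interest, or fat loss not a listed reaction.** Lipohypertrophy and lipoatrophy are in both lists; only narrow terms differ.
- **That hypertension drops out of a table meant to count it.** Attachment 4 defines no AEOI or ADR group and is tied to no table. Section 5.6 separately grades measured blood pressure and cross-tabulates the worst abnormality against reference.

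**Conclusion.** Attachments 2 and 3 are wrong as written, within narrow limits. The omission of the plain IRIS term from its own AEOI group is the clearest error, because Attachment 3 itself treats that term as a preferred term. DRESS comes next, on the assumption of a single version 20.0 preferred term. AGEP matters only under exact text matching, which the SAP neither specifies nor rules out. The fat tissue terms are a gap in a broad search on the AEOI side and an open question on the ADR side.

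The effect is at most one grouped table per affected event, plus, where the gap is in Attachment 2, the retrieval for medical review. The documents give no event counts, so the number of subjects affected cannot be estimated. No efficacy result is touched, and Section 5.4.2 plans no formal testing of adverse events. The point is worth acting on because it changes what the grouped safety tables count, and two of the terms are severe skin reactions. Attachment 4 calls only for a minor clarification.

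**What to change.** Before programming:

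1. Check Attachments 2 and 3 term by term against MedDRA 20.0, ideally from one shared term file.
2. Add the plain term *Immune reconstitution inflammatory syndrome* to the IRIS AEOI group.
3. Use the single version 20.0 preferred term for DRESS, and likewise for AGEP, in both lists.
4. Add *Fat tissue increased* to the Lipodystrophy AEOI, and confirm whether leaving *Fat tissue decreased* off the ADR list is intended.
5. As a minor clarification, state what Attachment 4 is for, remove the repeats of *Blood pressure abnormal*, and add plain *Hypertension* if the list is used to count blood pressure AEs.

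The cost is an edit to the attachments and to any term file built from them. Some grouped counts may rise slightly; the overall AE tables do not change.
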